#### **6.11.3.7. Completer Analyses**

The primary efficacy outcome, iADRS, from the dataset of those patients who remained in the study and on treatment through Week 104 (“completers”) will be analyzed using an ANCOVA. The change from baseline at Week 104 will be the dependent variable. The model will include the fixed, categorical effects of treatment, concomitant AChEI use at baseline (yes/no), pooled site, and the continuous effects of baseline iADRS score and age at baseline. The null hypothesis is that the differences in least-squares means between the LY3303560 dose groups versus placebo at Week 104 equal zero.

#### **6.11.3.8. Per Protocol Analyses**

The primary efficacy outcome, iADRS, from the per-protocol dataset will be analyzed using the DPM from the primary analysis. The change from baseline at each scheduled postbaseline visit will be the dependent variable. The model for the fixed effects will include the following terms

(same as primary efficacy analysis): baseline score, pooled site, treatment, visit, treatment-by-visit interaction, baseline-by-visit interaction, concomitant AChEI and/or memantine use at baseline (yes/no), and age at baseline. The null hypothesis is that the differences in least-squares means between the LY3303560 dose groups versus placebo at Week 104 equal zero.

#### **6.11.4. Other Secondary Efficacy Analyses**

The additional clinical and outcome measurements listed below will be analyzed separately using an MMRM analysis. The change from baseline at each scheduled postbaseline visit will be the dependent variable. The model for the fixed effects will include the following terms (same as primary efficacy analysis): baseline score, pooled site, treatment, visit, treatment-by-visit interaction, baseline-by-visit interaction, concomitant AChEI and/or memantine use at baseline (yes/no), and age at baseline. The null hypothesis is that the differences in least-squares means between the LY3303560 dose groups versus placebo at Week 104 equal zero. The outcomes that will be analyzed are:

- Change from baseline as obtained from the ADAS-Cog13
- Change from baseline in ADCS-ADL total score
- Change from baseline in ADCS-iADL score
- Change from baseline in ADCS-bADL score
- Change from baseline in CDR-SB
- Change from baseline in MMSE

## **6.12. Bioanalytical and Pharmacokinetic/Pharmacodynamic Methods**

### **6.12.1. Analysis of flortaucipir PET**

To evaluate the change from baseline in tau imaging parameters, an MMRM analysis will be used to compare change from baseline in SUVR at 104 weeks in the Evaluable Efficacy dataset. The model will include the fixed, categorical effects of treatment, visit, and treatment-by-visit interaction, as well as continuous effects of baseline SUVR and age at baseline. Visit will be considered a categorical variable with values equal to the visit numbers at which tau imaging is assessed. The null hypothesis is that the difference in LSM between the LY3303560 dose groups and placebo equals zero.

To assess the relationship of biomarker with cognition and function with treatment, Spearman's rank correlation coefficient will be obtained on change from baseline to Week 104 for the composite summary standard uptake value ratio (SUVR) normalized to bimodal white matter and with change from baseline to Week 104 for iADRS, ADAS-Cog13, ADCS-ADL, MMSE, and CDR-SB. Correlation analyses will be conducted using only patients who have the clinical outcome and SUVR result at Week 104 and include patients from all 3 dose groups.

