### 5.3. Method of Assignment to Treatment

Patients who meet all criteria for enrollment will be assigned a study (patient) number at Visit 1 and randomized to double-blind treatment at Visit 2. Patients will be randomized to LY3303560 or Placebo in a 1:1:1 ratio. Assignment to treatment groups will be determined by a computer-generated random sequence using an interactive web response system (IWRS). For the first, approximately, 30 patients, the IWRS will be programmed to guarantee balance between the arms for the first interim analysis for safety; this is referred to as the burn-in period. After the burn-in period, patient randomization will then follow the dynamic allocation (minimization) method of Pocock and Simon (1975) to balance the treatment arms using investigative site as a factor. This is to ensure balanced patient assignment between treatment arms within each site at the end of the study.

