## 6.2. Adjustments for Covariates

The repeated measures models will include the fixed, categorical effects of baseline score, pooled site, treatment, visit, treatment-by-visit interaction, baseline-by-visit interaction, concomitant AChEI and/or memantine use at baseline (yes/no), and age at baseline.

When an analysis of covariance (ANCOVA) model is used to analyze a continuous efficacy variable, the model will contain the main effects of treatment and appropriate baseline value included as a covariate. When an ANCOVA model is used to analyze a continuous safety variable, the model will contain the main effects of treatment, age, and appropriate baseline value included as a covariate.

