### **6.12.2. Analysis of NfL**

To evaluate the change from baseline in neurofilament light chain (NfL) concentrations, an MMRM analysis will be used to compare change from baseline between treatments up to 104 weeks of treatment in the Evaluable Efficacy dataset. All NfL values will be log transformed

prior to calculating baseline and change values. The model will include the fixed, categorical effects of treatment, visit, sex, and treatment-by-visit interaction, as well as continuous effects of log baseline, age, and log baseline-by-treatment interaction. Visit will be considered a categorical variable with values equal to the visit numbers at which NfL is assessed. The null hypothesis is that the difference in LSM between the LY3303560 dose groups and placebo equals zero.

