### **6.12.3. Analysis of Plasma Tau**

To evaluate the change from baseline in plasma tau concentrations (total tau and phospho tau 181), an MMRM analysis will be used to compare change from baseline between treatments up to 104 weeks of treatment in the Evaluable Efficacy dataset. All plasma tau values will be log transformed prior to calculating baseline and change values. The model will include the fixed, categorical effects of treatment, visit, sex, and treatment-by-visit interaction, as well as continuous effects of log baseline, age, and log baseline-by-treatment interaction. Visit will be considered a categorical variable with values equal to the visit numbers at which tau is assessed. The null hypothesis is that the difference in LSM between the LY3303560 dose groups and placebo equals zero.

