### **6.12.4. Analysis of vMRI**

Analyses of the following volumetric MRI (vMRI) parameters will be conducted (right + left for all but whole brain volume and ventricular volume):

- Hippocampal volume (cm^3)
- Entorhinal cortex (cm^3)
- Inferior parietal lobe (cm^3)
- Isthmus cingulate (cm^3)
- Lateral parietal lobe (cm^3)
- Medial temporal lobe (cm^3)
- Precuneus (cm^3)
- Prefrontal lobe (cm^3)
- Superior temporal lobe (cm^3)
- Cortical (cm^3)
- Whole temporal lobe (cm^3)
- Atrophy of total whole brain volume (cm^3)
- Enlargement of Ventricular volume (cm^3)
- White Matter (cm^3)
- White Matter Hypo Intensities (cm^3)

All of the above volumes are corrected for intracranial volume. To evaluate the changes in vMRI data after treatment, an MMRM analysis will be used to compare change from baseline to 104 weeks in the Evaluable Efficacy dataset. The change from baseline to the endpoint visit will be the dependent variable. The model will include the fixed, categorical effects of treatment, visit, and treatment-by-visit interaction, as well as continuous effects of baseline vMRI, baseline intracranial volume (ICV) and age. The null hypothesis is that the difference in LSM between the

LY3303560 active dose groups and placebo equal zero. A similar analysis will be performed for completers.

To assess the relationship of vMRI with cognition and function with treatment, Spearman's rank correlation coefficient will be obtained on change from baseline to Week 104 for vMRI parameters with change from baseline to Week 104 for iADRS, ADAS-Cog13, ADCS-ADL, MMSE, and CDR-SB; this will be performed using all patients who have the clinical outcome and vMRI result at Week 104; adjusted for age, baseline intracranial volume (ICV), and sex; and include patients from both treatment groups.

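### SAP 6.2 puts pooled site and AChEI/memantine use in the repeated measures models, but the tau PET, vMRI, NfL and plasma tau MMRMs omit both; the effect on inference is mild and conservative

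*SAP*

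**What the plan says.** **Allocation.** SAP 5.3 sets a 1:1:1 ratio. It starts with a burn-in ("For the first, approximately, 30 patients, the IWRS will be programmed to guarantee balance between the arms") and then uses minimisation "to balance the treatment arms using investigative site as a factor". No other balancing factor is named.

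**General rule.** SAP 6.2 states: "The repeated measures models will include the fixed, categorical effects of baseline score, pooled site, treatment, visit, treatment-by-visit interaction". The list goes on to baseline-by-visit interaction, AChEI and/or memantine use at baseline, and age. No endpoint is exempted.

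**Models that follow the rule on site.** Pooled site is in the primary disease progression model (6.11.1) and in the iADRS MMRM, slope and completer models (6.11.3.1, 6.11.3.6, 6.11.3.7). It is also in the clinical-scale MMRMs (6.11.4), the subgroup model (6.14) and the CBB and DCTClock MMRMs (6.17.1.1).

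**Models that do not.**
- Tau PET (6.12.1): "The model will include the fixed, categorical effects of treatment, visit, and treatment-by-visit interaction, as well as continuous effects of baseline SUVR and age".
- vMRI (6.12.4): treatment, visit and their interaction, "as well as continuous effects of baseline vMRI, baseline intracranial volume (ICV) and age".
- NfL (6.12.2): "fixed, categorical effects of treatment, visit, sex, and treatment-by-visit interaction, as well as continuous effects of log baseline, age, and log baseline-by-treatment interaction".
- Plasma tau (6.12.3): "The model will include the fixed, categorical effects of treatment, visit, sex, and treatment-by-visit interaction", with log baseline, age and log baseline-by-treatment.
- The second NfL and plasma tau MMRMs (6.17.2.1, 6.17.2.2): no site, and covariates that differ from those in 6.12.

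No reason is given for leaving site out.

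**The concern.** There are two problems, of unequal weight.

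The first is textual and does not depend on any assumption. Sections 6.2, 6.12 and 6.17.2 cannot all be followed for the same endpoint. Tau PET and vMRI carry two of the secondary objectives (SAP 4.2), and 6.1 has them tested two-sided at 0.05. Which covariates enter those models should be settled before anyone sees treatment codes. For NfL and plasma tau the document supports three covariate sets each: 6.2, 6.12 and 6.17.2.

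The second is statistical. When allocation balances a factor that explains outcome variance, a model without that factor leaves the between-site variance in the residual, although the allocation has largely removed it from the treatment contrast. The reported SE is then somewhat larger than the real sampling variability. Intervals are a little wide and tests a little conservative. The SAP takes minimisation seriously for inference elsewhere: 6.11.3.3 plans a randomization test to confirm the MMRM result. That test is listed only under the primary outcome, so the biomarker models have neither the balancing factor nor that check.

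**Working it through.** **1. Terms set side by side.** All models contain treatment, visit and treatment-by-visit.

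| Model | Pooled site | AChEI/memantine | Baseline-by-visit | Other terms |
|---|---|---|---|---|
| Rule in 6.2 | yes | yes | yes | baseline, age |
| Clinical scales, 6.11.4 | yes | yes | yes | baseline, age |
| Tau PET, 6.12.1 | no | no | no | baseline, age |
| vMRI, 6.12.4 | no | no | no | baseline, age, ICV |
| NfL, 6.12.2 | no | no | no | log baseline, age, sex, log baseline-by-treatment |
| NfL, 6.17.2.1 | no | no | no | log baseline, age |
| Plasma tau, 6.12.3 | no | no | no | log baseline, age, sex, log baseline-by-treatment |
| Plasma tau, 6.17.2.2 | no | no | no | log baseline |

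The conflict with 6.2 is therefore wider than site, and NfL and plasma tau also differ between 6.12 and 6.17.2.

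**2. No figure to reproduce.** The SAP states no SE, power or sample size for any biomarker model.

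**3. Theoretical limit.** With perfect balance within sites, the SE without site is too large by 1/√(1 − ICC), and the true level of a 5% test is 2Φ(−1.96/√(1 − ICC)). At ICC 0.05, 0.10 and 0.20 this gives an excess of 2.6%, 5.4% and 11.8%, and levels of 4.4%, 3.9% and 2.8%. The burn-in, small sites and dropout keep the trial short of this limit.

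**4. Simulation under the allocation of 5.3.**
- From the SAP: three arms 1:1:1, burn-in of 30 then minimisation on site, 30% dropout, 360 patients (5.2) or 225 (title page), two-sided 0.05.
- Assumed, because the SAP does not give them: 30 or 60 sites of unequal size, ICC 0 to 0.20, the favoured arm chosen with probability 0.8, dropout at random.
- Method: least squares on one Week 104 contrast, with and without site, 1,500 null trials per setting (Monte Carlo error of a 5% rate about 0.006). Individual sites were entered, not pooled sites.

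Mean SE in SD units and type I error, each without / with site:

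| Patients, sites | ICC | Mean SE | Change in SE from adding site | Type I error |
|---|---|---|---|---|
| 360, 30 | 0 | 0.1544 / 0.1588 | +2.8% | 0.043 / 0.041 |
| 360, 30 | 0.05 | 0.1541 / 0.1546 | +0.3% | 0.053 / 0.052 |
| 360, 30 | 0.10 | 0.1541 / 0.1505 | −2.3% | 0.046 / 0.055 |
| 360, 30 | 0.20 | 0.1533 / 0.1418 | −7.5% | 0.041 / 0.053 |
| 360, 60 | 0 | 0.1541 / 0.1642 | +6.6% | 0.053 / 0.045 |
| 360, 60 | 0.10 | 0.1544 / 0.1562 | +1.2% | 0.044 / 0.051 |
| 360, 60 | 0.20 | 0.1538 / 0.1471 | −4.4% | 0.039 / 0.051 |
| 225, 30 | 0 | 0.1954 / 0.2053 | +5.1% | 0.054 / 0.044 |
| 225, 30 | 0.20 | 0.1950 / 0.1834 | −5.9% | 0.041 / 0.055 |
| 225, 60 | 0 | 0.1959 / 0.2191 | +11.8% | 0.054 / 0.052 |

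Over all settings run, type I error without site was 0.039 to 0.057, and the model SE divided by the true sampling SD was 0.97 to 1.06. The combination of 225 patients and 60 sites was run only at ICC 0.

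**5. Scale in power terms.** No biomarker effect size is given, so the iADRS planning values in 5.2 serve as a yardstick only: 0.50 × 19.56 = 9.78 points, and 9.78/20.9 = 0.468 SD. With 360 patients and 30 sites (800 trials each), power without / with site was 0.85 / 0.82 at ICC 0 and 0.85 / 0.89 at ICC 0.20.

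**The case against.** The best defence is that 6.2 is a default. Its list matches the clinical-scale MMRMs term for term, while the biomarker models have their own terms (sex, ICV, log baseline-by-treatment). The SAP also departs from 6.2 elsewhere: 6.2 gives efficacy ANCOVAs only treatment and baseline, yet the completer ANCOVA in 6.11.3.7 adds site, age and AChEI use. This reading is reasonable, but the document does not state it. The ANCOVA paragraph of 6.2 separates efficacy from safety variables, so the authors limited a rule by type of variable when they meant to. The repeated measures sentence has no such limit.

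The second defence is that adding site may cost precision. This stands. At ICC 0 the SE rises by about 3% to 7% with 360 patients, and by about 5% to 12% with 225. The two models are close to break-even near ICC 0.05 with 30 sites, and only above 0.10 with 60. The SAP gives neither the number of sites nor the between-site variance. Pooling under 6.4 uses fewer terms than the simulation did, so it should cost less, but it also follows the balancing factor less closely.

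A reader might infer more than the document supports:
- **Levels down to 2.8% and an SE 11.8% too large.** These are perfect-balance limits. The simulated level at ICC 0.20 was about 4%.
- **Site as a stand-in for the scanner.** The SAP does not say where scans are done. The outcomes are changes adjusted for baseline, so a constant offset would largely cancel.

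**Conclusion.** The inconsistency is real and unconditional. Section 6.2 calls for pooled site and baseline AChEI/memantine use in the repeated measures models, the biomarker MMRMs in 6.12 and 6.17.2 contain neither, and NfL and plasma tau each have two different specifications.

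The statistical consequence is small and conditional. Omitting the balancing factor makes the SE at most mildly too large, in proportion to a between-site variance that the SAP does not give. At low ICC there is no detectable effect. At ICC 0.20 the level is about 4%, and adding site lowers the SE by roughly 4–8%. These sizes rest on the assumed site counts, ICC values and minimisation probability.

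A reader might also infer inflated false positives or a threat to the primary result. Neither follows. Any error is conservative, the biomarker tests are outside the gated graph in 6.11.2, and the primary model in 6.11.1 already contains pooled site. The point matters chiefly for tau PET and vMRI, which serve secondary objectives.

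**What to change.** Before unblinding, reconcile 6.2 with 6.12 and 6.17.2 in one of two ways.

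1. **Preferred.** Add pooled site, already derived under 6.4, as a fixed effect in the biomarker MMRMs, at least for tau PET and vMRI. Name the model without site as the fallback if the fit does not converge. State whether AChEI/memantine use and baseline-by-visit apply to these endpoints, since adding site alone would leave the conflict with 6.2.
2. **If the omission is deliberate.** Limit the repeated measures sentence in 6.2 to the clinical scales, give the reason, and prespecify the pooled-site model as a sensitivity analysis.

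In either case, give NfL and plasma tau one covariate list each and remove the duplicate specification.

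The cost is SAP wording and one existing variable. The statistical downside of the first option, if site explains no variance, is an SE about 3% (30 sites) to 7% (60 sites) larger with 360 patients, and more with 225. If many small sites remain after pooling, that favours the second option for NfL and plasma tau.

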### 5.2. Determination of Sample Size

Based on the Disease Progression Model (DPM), 360 enrolled patients, a 30% dropout rate, and a 3-month delay of treatment effect onset, this sample size will provide more than 95% power to

demonstrate that at least one of the active treatment arms has slowed cognitive/functional decline. This claim of slowing cognitive/functional decline is based on showing that at least one of the active treatment arms has a  $\geq 0.6$  posterior probability of slowing of iADRS progression over placebo by at least 4 points (that is, 25% slowing relative to placebo, based on a mean change from baseline in the placebo group of 16 points and mean change from baseline on at least one of the active treatment arms of at most 12 points) after 104 weeks (approximately 24 months) on study treatment. This power calculation comes from simulations using a placebo decline of 19.56 points and 33% slowing on 1400 mg LY3303560 and 50% slowing on 5600 mg LY3303560 relative to placebo at 104 weeks. The variance-covariance matrix in the simulations had a variance at Week 104 of 436.85 (equal to a standard deviation of 20.9). If both active treatment arms are placebo-like with no efficacy, the probability of passing the efficacy criterion specified above (that is, false positive) is approximately 2.5%. To test the hypothesis of a disease progression benefit, we calculate the posterior probability of superiority in cognitive/functional slowing, and if it is above a pre-specified threshold (which controls the experiment-wise type I error at approximately 2.5%), then a claim of cognitive slowing will be made. The simulation for the power calculation and sample size determination was carried out in FACTS Version 5.5.

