## 6.17.2. *Exploratory Bioanalytical and PK/PD Analyses*

### 6.17.2.1. Analysis of Neurofilament Light Chain (NfL)

To evaluate the change from baseline in Neurofilament Light chain (NfL), an MMRM analysis will be used to compare change from baseline at 104 weeks in the Evaluable Efficacy dataset. The model will include the fixed, categorical effects of treatment, visit, and treatment-by-visit interaction, as well as continuous effects of baseline log(NfL) and age at baseline. The NfL values will be log transformed prior to calculating the changes from baseline. Visit will be considered a categorical variable with values equal to the visit numbers at NfL is assessed. The null hypothesis is that the difference in LSM between the LY3303560 dose groups and placebo equals zero.

Change from baseline and annualized change from baseline analyses will be conducted on NfL. The annualized change will be compared between the treatment groups with an ANCOVA on the full efficacy dataset. The ANCOVA model will include the fixed effect of treatment as well as continuous effects of baseline NfL value and age at baseline. The null hypothesis is that the difference in LSM between the LY3303560 dose groups and placebo equal zero.

To assess the relationship of biomarker with cognition and function with treatment, Spearman's rank correlation coefficient will be obtained on change from baseline to Week 104 for the NfL and with change from baseline to Week 104 for iADRS, ADAS-Cog13, ADCS-ADL, MMSE, and CDR-SB. Correlation analyses will be conducted using only patients who have the clinical outcome and SUVr result at Week 104 and include patients from all 3 dose groups.

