### 6.17.2.2. Analysis of Plasma Tau

To evaluate the change in plasma tau analytes (including assayed plasma total tau and p-tau) after treatment, an MMRM will be used to compare change from baseline to 104 weeks. The plasma tau values will be log transformed prior to calculating the changes from baseline. This analysis will be run separately for each plasma tau parameter using the Evaluable Efficacy dataset. The model will include the fixed, categorical effects of treatment, visit, and treatment-by-visit interaction, as well as the continuous effect of baseline log(plasma tau). Visit will be considered a categorical variable with values equal to the visit numbers at which plasma tau is assessed. The null hypothesis is that the difference in LSM between the LY3303560 dose groups and placebo equal zero. A similar analysis will be performed for completers.

To assess the relationship of plasma tau with cognition and function with treatment, Spearman's rank correlation coefficient will be obtained on change in plasma tau from baseline to Week 104 and with change from baseline to Week 104 for iADRS, ADAS-Cog13, ADCS-ADL, MMSE, and CDR-SB. Correlation analyses will be conducted using only patients who have the clinical outcome and plasma tau result at Week 104.

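### The biomarker-clinical correlations name no by-arm or treatment-adjusted coefficient, so a pooled value would mix any between-arm drug shift with the patient-level association

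*SAP*

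**What the plan says.** Four SAP sections plan Spearman correlations between Week 104 change in a biomarker and Week 104 change in iADRS, ADAS-Cog13, ADCS-ADL, MMSE and CDR-SB. All four give the aim in near-identical terms; the NfL version reads "To assess the relationship of biomarker with cognition and function with treatment".

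- **Tau PET (6.12.1):** patients need a clinical outcome and an "SUVR result at Week 104 and include patients from all 3 dose groups".
- **NfL (6.17.2.1):** again a "result at Week 104 and include patients from all 3 dose groups".
- **vMRI (6.12.4):** the correlation is "adjusted for age, baseline intracranial volume (ICV), and sex; and include patients from both treatment groups". Treatment is not in the adjustment set, and the trial has three arms (5.1, 5.3).
- **Plasma tau (6.17.2.2):** "Correlation analyses will be conducted using only patients who have the clinical outcome and plasma tau result at Week 104". Nothing is said about arm.

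No section asks for a coefficient by arm, a stratified coefficient or an adjustment for treatment. The repeated-measures models for the same biomarkers, in the same sections, do include treatment.

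**The concern.** Arm can influence both variables in each correlation. The trial tests for drug effects on tau PET and vMRI (SAP 4.2) and on plasma tau, ptau217 and NfL (SAP 4.3), and its power calculation assumes a clinical effect at both doses (SAP 5.2). If the arms differ on both variables, the pooled cloud of points has a slope made partly of the distance between arm means. A reader would naturally take the coefficient to say that patients whose biomarker changed more also declined differently, when it may only restate that the arms differ. If the drug moves the biomarker alone, the extra between-arm spread adds noise and pulls a real association towards zero.

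At stake is the interpretation of a supportive pharmacodynamic result. The distortion grows with the drug effects that the trial was designed to look for.

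**Working it through.** The SAP gives no expected coefficient, power or sample size for these correlations, so it has no figure to reproduce. The one related check is √436.85 = 20.9, which agrees with SAP 5.2.

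**Inputs from the SAP**
- Allocation: "Patients will be randomized to LY3303560 or Placebo in a 1:1:1 ratio" (5.3).
- Size: "360 enrolled patients, a 30% dropout rate, and a 3-month delay of treatment effect onset" (5.2). 360 × 0.70 = 252, or 84 per arm. The title page gives about 225 patients: 225 × 0.70 / 3 ≈ 52 per arm. Both are carried as a range.
- Clinical effect (5.2): placebo decline 19.56, slowing 33% and 50%, SD 20.9. Shifts: 0.33 × 19.56 / 20.9 = 0.31 SD and 0.50 × 19.56 / 20.9 = 0.47 SD.

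**Assumed inputs**
- High-dose biomarker shift from 0.25 to 2 SD, low dose at half.
- Within-arm correlation ρ of 0 or ±0.3.
- Two-sided 0.05 as a yardstick. SAP 6.1 sets that level for pairwise treatment tests, not for correlations.

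**Formula.** With equal arms and variables in within-arm SD units, the pooled correlation is

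(ρ + C) / √[(1 + Vx)(1 + Vy)],

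where Vx and Vy are the between-arm variances of biomarker and clinical change, and C is their between-arm covariance.

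**Example: biomarker shifts 0, 1, 2 SD and clinical shifts 0, 0.31, 0.47 SD**
- Vx = (1 + 0 + 1)/3 = 0.667
- Clinical mean 0.26, deviations -0.26, 0.05, 0.21, so Vy ≈ 0.038
- C = [(-1)(-0.26) + 0 + (1)(0.21)]/3 ≈ 0.156
- ρ = 0: 0.156 / √(1.667 × 1.038) = 0.156 / 1.315 = 0.119
- ρ = -0.3: (-0.3 + 0.156) / 1.315 = -0.11

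Rough check of the rejection rate at 252 patients: 0.119 × √251 = 1.89, and Φ(1.89 - 1.96) ≈ 0.47.

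**Simulation** (1,500 trials per scenario; the stratified coefficient is the Fisher-z mean of the three within-arm Spearman values).

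No within-arm link, SAP clinical effect:

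| High-dose biomarker shift | Pooled coefficient | p<0.05, 52 per arm | p<0.05, 84 per arm |
|---|---|---|---|
| 0.5 SD | 0.04 | 7% | 9% |
| 1 SD | 0.07 | 15% | 19% |
| 2 SD | 0.12 | 34% | 47% |

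At 0.25 SD the pooled coefficient is about 0.02 in absolute value, with 5.5% rejection at 52 per arm. That is within simulation error of 5%, since √(0.05 × 0.95 / 1500) ≈ 0.6 percentage points. The stratified coefficient averages about 0, with rejection of 3-6%, throughout.

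Within-arm ρ = -0.3, SAP clinical effect, between-arm shift in the opposite direction:

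| High-dose biomarker shift | Pooled coefficient | Detected, 52 per arm | Detected, 84 per arm |
|---|---|---|---|
| 0.5 SD | -0.24 | 86% | 97% |
| 1 SD | -0.19 | 66% | 86% |
| 2 SD | -0.09 | 21% | 30% |

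The stratified coefficient stays near -0.29, with detection of about 93-95% at 52 per arm and over 99% at 84. When the between-arm shift runs the same way as the within-arm link (ρ = +0.3), the pooled value is instead mildly inflated: 0.33 against 0.29 at 2 SD.

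Biomarker shift with no clinical effect: for ρ = 0 nothing is created (rejection about 5%). For ρ = -0.3 and a 2 SD shift, the pooled value falls to -0.22. Detection is then 94% at 84 per arm (stratified over 99%) and about 80% at 52 per arm (stratified 96%).

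**The case against.** Much of the case on the other side stands.

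- **The wording is about who is included.** Listing all three groups does not rule out by-arm output, and plasma tau leaves the matter open. One might infer that the SAP states a single pooled coefficient in all four places. It does not. Pooling is the natural reading for tau PET and NfL, implied for vMRI and unstated for plasma tau. What remains is that no section specifies anything else.
- **The SAP does not predict biomarker movement.** A reader might take the plasma tau objectives in 4.3 as an expected effect. They set out to assess one, with no direction or size, and each repeated-measures model has a null of zero difference.
- **A biomarker shift alone creates nothing.** It only dilutes. An association without a within-arm link appears only when the arms also differ clinically, as the SAP's planning scenario assumes.
- **The rejections are not false positives in the strict sense.** If the drug moves both variables, they are associated across the trial population, and a pooled coefficient is a fair description of that co-movement. It misleads only when read as a patient-level link. The stated aim does not say which is wanted.
- **No test or surrogacy claim is planned.** The correlations have no null hypothesis, alpha or decision rule, so the rejection rates are a yardstick. One might infer that a surrogate conclusion would be wrong, but the SAP draws none.
- **By-arm coefficients could be added anyway**, since 6.1 allows further exploratory analyses. That is true, but results chosen after unblinding carry less weight than prespecified ones.

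**Conclusion.** The point holds as a low-cost improvement to supportive analyses. As written, the four sections do not separate the patient-level association from a between-arm shift, and where pooling is the natural reading the two would be mixed.

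The size rests on a biomarker shift that the SAP does not give. It is negligible at 0.25 SD, small at 0.5 SD and material from about 1 SD in the high-dose arm, given the SAP's planned clinical effect and bivariate-normal data. The distortion can inflate, create or mask, depending on the direction of the between-arm shift relative to the within-arm link.

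These correlations lie outside the multiplicity graph (6.11.2), and NfL and plasma tau sit under the planned exploratory analyses (6.17). The treatment effects on the biomarkers come from models that include arm. Primary, gated and safety inference is unaffected.

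Separately, the vMRI text refers to two treatment groups in a three-arm trial, so its correlation population is unclear.

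**What to change.** In 6.12.1, 6.12.4, 6.17.2.1 and 6.17.2.2:

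1. Report Spearman's coefficient within each of the three arms.
2. Add one treatment-stratified summary: a Fisher-z combination of the within-arm values, or a partial Spearman coefficient with arm indicators. The partial form fits vMRI best, where covariates are already adjusted for.
3. Keep the pooled coefficient, labelled as descriptive of overall co-movement.
4. In 6.12.4, replace the reference to two groups with all three treatment arms.

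The cost is a few sentences and a few lines of code, with no new data. The per-arm coefficients have wider intervals. The stratified summary loses almost nothing: with no shifts and ρ = -0.3, detection is 94% against 95% pooled at 52 per arm, and over 99% for both at 84.

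The NfL sentence in 6.17.2.1 also selects patients on a tau PET result rather than an NfL result. That is a separate wording matter, but the same edit can settle it.
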